What are the research activities this person will be responsible for: Study Coordinator; Ethics submissions, placing advertisements, recruitment, assisting entry of participants into trial, data collection/measurement of parameters in the trial (except those associated with Ultrasound Doppler which will be carried out by a Sonographer), data entry, preparation of data for analysis	
Does this person have a current Good Clinical Practice certificate that you will submit with your application?  Yes /  No - Good Clinical Practice training is required by all listed investigators, as per National Clinical Trials Governance Framework action 1.2 and 1.6	
Contact details: a Health or University email address must be used  I am the contact person for this project	[contact] Email: [contact]

Research Overview

Please provide a brief overview of the study:

Recruit and conduct a single site randomised controlled crossover clinical trial of the impact of 3 weeks home use of **Niagara® Cycloid®** massage pad action on chronic unilateral chronic oedema/lymphoedema of the legs arising as a consequence of treatment for cancer of the bowel, other abdominal structures (including ovaries and prostate) and melanoma. There will be a follow up period at 2 weeks and at 1 month. The massage pad is a TGA-approved medical device, class IIa (ARTG 151788).

Background and literature review

Correctly and externally applied vibration is widely regarded as having a potential for bringing about improvements in a range of health disorders and conditions as well as when there are undiagnosed or un-recognised pathologies. Human studies have shown that cycloid vibration therapy (CVT) applied externally to the skin can increase venous and arterial blood flow and the movement of interstitial fluid in people with lymphoedema (swelling caused by abnormal accumulation of lymph fluid). This increased local area blood flow may assist in the reduction of lymphoedema, musculoskeletal pain and improve joint mobility. In turn, improving quality of life and general wellbeing.

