Estimated sample size of 30 final participants based on our current best knowledge based on prior trials of the pad we have conducted.

Methodology - clearly describe the specific procedures or techniques that will be used to answer the research question and meet the aims.

Participants will be randomly allocated into either the treatment or control group by odd vs even number selection. In the control group, participants will conduct their normal lymphoedema care routine. In the treatment group, the participant's lymphoedematous leg will be treated with the Niagara® Cyclopad for a total of 30 minutes (i.e. 10 minutes each in three locations; lower back, upper leg and lower leg) using the set minimum frequency. There will be 5 cycles of deep breathing before and after the massage pad use. Participants will be asked to rest supine for 15 mins prior to starting each treatment. At the end of their 4-week follow-up period, the participant will be crossed over into the other group.

Measurement points are:

- Screen
- Baseline
- Day 1/2 (phone call)
- Day 4
- 1 week
- 2 weeks
- 3 weeks
- 2 weeks Follow-up
- 4 weeks Follow-up

Please see Table 1 for Schedule of assessments.

Procedure	SCREEN	BASELINE	PHONE CALL (Day 1 or 2)	DAY 4	WEEK 1	WEEK 2	WEEK 3	FOLLOW-UP 1 (2 weeks)	FOLLOW-UP 2 (4 weeks)	
			Treatment or Control Phase						Post-Treatment/Control Phase	
Visit	1	2	3	4	5	6	7	8	9	
Informed Consent	✓									
Eligibility Criteria	✓									
Demographics	✓									
Medical History	✓									
Physical Exam	✓	✓								
Vital Signs	✓	✓		✓	✓	✓	✓	✓	✓	
Height	✓	✓								
Weight	✓	✓		✓	✓	✓	✓	✓	✓	
LYMQOL		✓					✓	✓	✓	
Symptom Scale (10-point Likert)		✓					✓	✓	✓	
Bioimpedance	✓	✓		✓	✓	✓	✓	✓	✓	
Limb Volume	✓	✓		✓	✓	✓	✓	✓	✓	
MoistureMeter D		✓		✓	✓	✓	✓	✓	✓	
Tonometry/Skin FibroMeter		✓		✓	✓	✓	✓	✓	✓	
Concomitant Medications	✓	✓		✓	✓	✓	✓	✓	✓	
Review Participant use of device in-situ			✓							
Review Participant Diary			✓	✓	✓	✓	✓			
Sonography		✓					✓	✓		

crossover to other group

Procedure	BASELINE	PHONE CALL (Day 1 or 2)	DAY 4	WEEK 1	WEEK 2	WEEK 3	FOLLOW-UP 1 (2 weeks)	FOLLOW-UP 2 (4 weeks)	
			Treatment or Control Phase					Post-Treatment/Control Phase	
Visit	10	11	12	13	14	15	16	17	
Informed Consent									
Eligibility Criteria									
Demographics									
Medical History									
Physical Exam	✓								
Vital Signs	✓		✓	✓	✓	✓	✓	✓	
Height	✓								
Weight	✓		✓	✓	✓	✓	✓	✓	
LYMQOL	✓					✓	✓	✓	
Symptom Scale (10-point Likert)	✓					✓	✓	✓	
Bioimpedance	✓		✓	✓	✓	✓	✓	✓	

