How are potential participants identified as suitable for the research?

Advertisement notice attached separately. Participants will be recruited from the local lymphoedema clinics and by word of mouth from those who decided to participate. Advertisement will be placed on relevant notice boards in clinics. All will be provided with the full details (see PICF) if they express verbal interest.

How will participants be recruited into the study?

Potential participants will see advertisement and then on the basis of that decide if they wish to participate. We anticipate some interest by word of mouth and in these cases the potential participant will be provided with the advertisement, followed by the PICF if still interested.

Who is approaching the participants about this research project?

Self-identification through awareness of the ad or Lymphoedema Therapist will notify a potential participant of the study.

When is this occurring?

Clinic – a lymphoedema therapist will notify the potential participant that the trial is available.

Are participants reimbursed for parking, travel or time involved?

- No
 Yes

Please detail what is being reimbursed and the amount:

Participants will be reimbursed \$10 for parking and provided a \$10 gift voucher for a light meal or drink at a local café. Participants will be able to keep the massage pad provided to them during the trial at the end of the study.

Participant commitment -

Participants will have 17 appointments over the full crossover study design (from screening to 4 week follow-up). Two of these visits will be a phone call (Day 1 or 2). Assessments are non-invasive and outlines in the Methodology Section.

Participant follow up –

Participants have clinic appointments at Screening, Week 1, Week 2, Week 3, 2-week Follow-Up and 4-week Follow-Up (for both the treatment and control arm). There will be a phone call on Day 1 or Day 2 to monitor progress and home use of the massage pad.

Ethical considerations

Please describe the risk and burden associated with your research.

This research is of no risk of harm or discomfort and no risk for minor burden or inconvenience. The only foreseeable risk is no greater than discomfort. The massage pad is a TGA-approved medical device, class IIa (ARTG 151788) and the assessments are non-invasive. There is a risk the quality of life questionnaire (LYMQL) may cause distress. Counselling will be provided if required.

How will any risks be managed?

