Matching and sampling strategies: Participants will be randomly allocated into either the treatment or control group by odd vs even number selection. After the 4 week follow-up period, the participants will be crossed over into the other group (treatment or control). In the event a participant does not wish to participate in the second group then either another participant who intends to participate in both will be chosen or a second participant chosen with matching bio data (Age, gender, BMI).
Accounting for potential bias, confounding factors and missing information: Randomisation will help avoid bias. We will also be able to observe if there are conditions such as psoriasis, infection etc on the limbs and exclude participants if not declared in initial responses. Missing information is unlikely due to the short time of the intervention and measurement period. Should it occur due to equipment failure then the participant could be invited to return. Failing this the data set would be excluded from the analysis
Sample size and statistical or power issues –

This study is one following information collected from a prior pilot trial and has informed us a sample size of 30 is adequate. While a statistical outcome is useful, we also will examine what we see as “biological” or “practical” changes. However, given the relative homogeneity of the sample and the fact that we do not intend to undertake or rely on any subgroup analysis the sample size of 30 is adequate. The equipment we use i.e., perometry is able to accurately and detect changes in limb volumes of 50ml in a 5000ml limb section and our Bio-impedance analysis unit can detect fluid changes of 10ml per limb.

How will you measure, manipulate and/or analyse the information collected?

All data will be used in its raw form as generated by the measuring equipment. Analysis initially by excel and followed by analysis using STATA or similar statistical program as appropriate.

Data linkage – what linkages are planned or anticipated?

None

Participants may withdraw from the study by choice, what impact will a participant withdrawing have on the data?

Should they withdraw, they will be replaced by another matched participant completely or for the arm of the trial that they withdrew from. Given the massage pad is available on the market and this is low risk research, we don't anticipate many participants to withdraw.

How will this be responded to?

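### No step retrieves the massage pad after its 3 weeks of use, and any use during the follow-up windows goes unrecorded

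*Protocol*

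**What the plan says.** The Research Overview describes a "single site randomised controlled crossover clinical trial of the impact of 3 weeks home use of" the pad. Under Methodology, control is usual care: "In the control group, participants will conduct their normal lymphoedema care routine". The only washout is the follow-up period: "At the end of their 4-week follow-up period, the participant will be crossed over into the other group". Under Participant selection and activities, the answer on reimbursement adds: "Participants will be able to keep the massage pad provided to them during the trial at the end of the study".

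Table 1 has two rows that bear on pad use:

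- "Review Participant use of device in-situ" is ticked only at the Day 1/2 call of each cycle (Visits 3 and 11).
- "Review Participant Diary" is ticked from that call to Week 3 of each cycle (Visits 3 to 7 and 11 to 15). It is not ticked at Follow-up 1 or 2 (Visits 8 and 9, 16 and 17) or at the second baseline (Visit 10).

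Table 1 has no row for issuing, returning or collecting the pad. No section tells participants to stop using it during follow-up or control. What the diary records is not described.

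**The concern.** The pad is used at home without supervision. A crossover needs the treatment to be absent from the control period, and the follow-up visits are informative only if treatment stopped at Week 3. The protocol implies both conditions by calling the intervention 3 weeks of use, but nothing in its conduct secures or verifies them.

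Two results are at stake. The measurements 2 and 4 weeks after treatment are meant to show whether a change lasts. If some participants go on using the pad and nobody records it, a lasting effect cannot be told from continued treatment, and this applies to both sequences. Second, a treatment-first participant can carry the pad into the control period, whereas a control-first participant has no trial pad before the second period. Any contamination of the control period by the trial pad therefore falls on one sequence only, and randomisation does not remove it.

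**Working it through.** **Plan's own figure.** The only related figure is "Estimated sample size of 30 final participants". It cannot be reproduced. The Analysis section says "This study is one following information collected from a prior pilot trial and has informed us a sample size of 30 is adequate" but gives no significance level, power, effect size or SD. The detection limits quoted there for perometry and bioimpedance describe instruments, not variation between participants.

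**Time the pad could be held.** From Table 1, for a treatment-first participant after the intended stop at Visit 7:

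- washout 4 weeks + control 3 weeks = 7 weeks to the end of the control phase;
- 7 + 4 weeks of second follow-up = 11 weeks to Visit 17.

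Diary review covers the 3 control weeks and neither 4-week follow-up window.

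**Effect on the comparison.** Let τ be the true effect at the end of 3 weeks' use, and f the fraction of τ present in the control period of the treatment-first sequence, averaged over its participants. The documents give no value for f, so the full range 0 to 1 is an assumption. Take the estimate as the equal-weight mean of the two sequences' treatment-minus-control differences, which cancels a common period effect, and assume no other carryover. The control-first sequence contributes τ throughout.

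1. *End-of-period values (Visit 7 against Visit 15).* The treatment-first sequence contributes τ - fτ. Mean: [(τ - fτ) + τ]/2 = τ(1 - f/2).
2. *Change from each period's baseline, steady use through washout and control.* Visits 10 and 15 both carry fτ, so the control change is fτ - fτ = 0. Mean: (τ + τ)/2 = τ.
3. *Change from baseline, use in washout that stops when control begins, effect gone by Visit 15.* The control change is 0 - fτ. Mean: [(τ + fτ) + τ]/2 = τ(1 + f/2).

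| f (assumed) | 1. End-of-period | 2. Change, steady use | 3. Change, use stops at Visit 10 |
|---|---|---|---|
| 0 | 1.000 τ | 1.000 τ | 1.000 τ |
| 0.25 | 0.875 τ | 1.000 τ | 1.125 τ |
| 0.50 | 0.750 τ | 1.000 τ | 1.250 τ |
| 0.75 | 0.625 τ | 1.000 τ | 1.375 τ |
| 1.00 | 0.500 τ | 1.000 τ | 1.500 τ |

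The same behaviour by participants can thus shrink the estimate, leave it unchanged or enlarge it, depending on when the pad is used and which contrast is analysed. The protocol does not fix the contrast.

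**The case against.** The strongest reply is that this rests on silence. The promise to keep the pad takes effect at the end of the study, which is compatible with collection after Week 3 and re-issue later. Table 1 has no row for handing the pad out either, so it may simply not track device logistics. The participant information and consent form is not shown and may deal with return. The protocol also bounds use to 3 weeks, labels what follows as a post-treatment phase and defines control as usual care, so pad use outside the treatment period would be non-adherence, not something the design permits. The control phase is monitored, and Visit 10 repeats limb volume, bioimpedance, moisture, tonometry, quality of life, symptoms and sonography.

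Much of this stands. A reader might infer that the protocol leaves the pad in the home between periods, or allows its use under control; the text says neither. A reader might also infer that the limb's state at crossover goes unchecked. It is measured in full at Visit 10, and a comparison with Visit 2 can be left to the statistical analysis plan.

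What the reply does not remove is that no retrieval step is written and that the two 4-week follow-up windows have no scheduled diary review. Both are matters of conduct. An analysis plan cannot recover pad use that was never recorded.

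**Conclusion.** The point holds as a gap in conduct. Treatment-first participants may hold a working pad for up to 7 weeks beyond its intended use by the end of their control phase, and use in either follow-up window would not be captured. If such use occurs, the 2- and 4-week results after treatment cannot be interpreted, and the treatment-control comparison is exposed to bias through one sequence only.

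The size is conditional. With end-of-period values the estimate loses f/2 of the effect, at most half. With change from the Visit 10 baseline there may be no bias, or an inflation of up to f/2. A reader might infer that the effect is always pulled towards zero; the second and third cases above show otherwise. A reader might also want a figure for lost power, but it would have to start from an assumed design power, significance level and standardised effect, none of which the protocol states. How many participants would go on using the pad is likewise unknown.

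**What to change.** - Collect the pad at the Week 3 visit of the treatment period (Visit 7 for treatment-first, Visit 15 for control-first) and return it to keep at Visit 17. This honours the promise to participants and states where the pad is between Week 3 and the end of the study.
- Extend the diary-review row of Table 1 to both follow-up visits of each cycle (Visits 8, 9, 16 and 17), with one question on any pad use since the last visit. Asking about any pad is sensible because the Analysis section notes that the device is on sale.

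Cost: both changes use visits that already exist and add one question. The small downside is that participants must carry the pad to the clinic and wait to keep it.

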Measurements are described above in Methodology Section. The outcome will be an improved understanding of the impact of CVT on the blood flow into and out of lymphoedematous legs and of its impact on overall leg and fluid volumes. As well as perceived impact of the participant on symptoms and quality of life and use of the device.

Inclusion criteria –

Clinically diagnosed Chronic oedema/lymphoedema (arising from treatment for cancer) of one leg, more than 1.5 years duration but less than 10 years duration

Age group 45-75,

Male or Female

BMI classes: Overweight 25-29.9 and Obese Class I (Moderately obese) 30-34.9

Exclusion Criteria –

Clinically diagnosed thyroid disorder (nor medications for it)

Venous issues of the legs including venous reflux, significant varicosities or signs of venous disorder/disease (LDS, Haemosiderin in over large areas) Spider veins and minor superficial venous telangiectasia ok)

Leg swelling prior to the intervention for cancer (statement from the referring clinician about this)

Medications likely to have an influence on sodium retention such as Beta blockers, Diuretics

Current wounds/ulcers on the legs

Signs of significant recent soft tissue wounding

Signs of current skin breakdown.

Abnormal liver, renal and heart function

Current or recent (< 1 month) bacterial infections (Cellulitis)

Pregnant

Cardiac pacemaker

large metal plates/implants

Funding

Please provide a brief explanation:

Funding source: Sponsor - Niagara® CT Health Care

Funding amount: \$ \$11,870.55 per trial participant

Who will manage the study budget? Lymphoedema Clinical Research Unit, Flinders University

Is there additional funding support provided by an external source? No

Storage of blood and/or tissue samples

Not applicable for this research study

Consent

How you will be obtaining consent and/or what alternatives you will be using?

Written consent after the provision of the PICF to potential participants. Potential participants will have at least a week to read the PICF and consider the study and discuss with their GP/Family, before then obtaining consent at an appointment. The consenting appointment will allow for time to answer any further questions. This is a low-risk study given non- invasive measurements.

Please advise (by name) which investigators will provide the information sheet and consent form to the participant?

Study Coordinator – [name]

Please advise (by name) investigators who will obtain consent?

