Participant is free to withdraw from the study if they find the treatment discomforting.

Benefits – please identify and explain the expected outcomes and benefits of the study

The outcome will be an improved understanding of the impact of CVT on the blood flow into and out of lymphoedematous legs and of its impact on overall leg and fluid volumes. As well as perceived impact of the participant on symptoms and quality of life and use of the device.

Does a dependant or unequal relationship exist between the participant and the researcher?

- Yes -
How will the dependant / unequal relationship be managed?
 No

Conflicts of interest: Please refer to the National Statement chapter 5.4, and your institutional policy for guidance.

- Yes / No

Please provide details of the conflict of interest and how it will be managed:

Data management plan

Which listed investigators will collect the study data / information?

SC will collect all data and enter into an Excel spreadsheet (located on Flinders University password-protected computer drive). Sonographer will collect ultrasound data and SC will enter this into the spreadsheet.

What type of data will be used?

- Data that has never been labelled with individual identifiers or from which identifiers have been permanently removed, and by means of which no specific individual can be identified.
- Identifiable - data that contains an identifier or combination of identifiers i.e. name, date of birth, image, address, URN
- Data in which identifiers have been removed and replaced by a code, but it remains possible to re-identify a specific individual by, for example, using the code or linking different data sets.

If the data being used has the potential to identify a patient, please justify and describe how accidental re-identification will be avoided?

Any identifying codes will be removed and replaced by numbers only.

If the participant's medical records are being accessed - please state where the information is being collected

N/A

Data sets -

Ultrasound doppler – flow rates, flow volumes from major artery and veins on both legs, as per the data output from the Doppler unit. This is then transcribed into an excel data sheet.

Perometry - the total volume and circumferences of both limbs are noted from the perometry program and transcribed into the excel data sheet.

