Once the participant has let the research team know that they wish to withdraw, the withdrawal will be documented. If the participant wishes a follow-up on lymphoedema status, this will be conducted. A participant may provide the research team with the reason(s) for leaving the study, but is not required to provide their reason.

Results, reporting, outcomes, and future plans

Please detail your plans for the return of the research results to the participants:

Participants will be given a copy of the data gained from the Perometer, the BIS analyser (giving them details of their BMI, muscle, fats, fluids and a fitness score similar to those given at gyms) at the end of each clinic appointment. They will also be given a copy of the overall study results.

What are your plans for dissemination and publication of project outcomes?

We would intend to present research outcomes at the Australasian Lymphology Association meeting in 2025 as it has relevance to disorders such as lymphoedema and chronic oedema.

Will you be providing a de-identified data set to the journal for verification purposes?

All data collected is de-identified and will have a re-identification code so that the remaining information does not identify an individual.

Please detail other potential uses of the data at the end of the project:

Inform us of what benefits might come from massage pad use in lymphoedema at the base frequency setting.

What are your plans for sharing and/or future use of data and/or follow-up research? i.e., anticipated secondary use of data:

If results are publishable and presentable, we plan to share with publications and conferences; including conferences with community engagement. De-identified results will be shared with Sponsor. The results will inform us on the direction of any future research in this area, including if vibration therapy, an easily applied, non-invasive therapy, can optimise outcomes for lymphoedema management. If a benefit is measured, infrared and indocyanine green imaging studies would be considered to detail the response of the lymphatics through location and function before and after treatment, as well as research of the effect of this therapy on other lymphatic conditions.

What is the project closure process?

Final HREC report and report to the sponsor. Destruction of the data after 5 years.

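### No systematic adverse-event or device-incident recording is scheduled, so harms of the home-used pad would be seen only indirectly, and the protocol's risk statements conflict

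*Protocol*

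**What the plan says.** **Risk.** The Ethical considerations section opens with "This research is of no risk of harm or discomfort and no risk for minor burden or inconvenience". The next sentence is "The only foreseeable risk is no greater than discomfort", and the same paragraph adds "There is a risk the quality of life questionnaire (LYMQL) may cause distress", with counselling offered if needed. The answer on how risks are managed is "Participant is free to withdraw from the study if they find the treatment discomforting". The Consent section says "This is a low-risk study given non- invasive measurements".

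**Collection.** Participant commitment states "Participants will have 17 appointments over the full crossover study design (from screening to 4 week follow-up"), two of them phone calls. Table 1 (Schedule of Assessments) lists what is done at each contact. It has rows for vital signs, concomitant medications, diary review, a symptom scale and a review of device use, but none for adverse events or device incidents. The Data sets section lists Doppler, perometry, bioimpedance, indurometry, the two questionnaires and feedback.

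**Withdrawal.** Under Analysis: "Should they withdraw, they will be replaced by another matched participant completely or for the arm of the trial that they withdrew from". The following answer says the withdrawal is documented and that a participant may give a reason, "but is not required to provide their reason". The recruitment target is 30 final participants.

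**The concern.** The trial puts a device into people's homes for daily use over three weeks after cancer treatment, and compares it with their normal lymphoedema care. A reader of the results will ask how many people had a problem with the pad, what it was, and whether it was more frequent than under usual care. If the schedule is followed exactly, no contact asks that question in a form that can be counted by condition. The people most informative about tolerability, those who stop partway, leave the least information. Replacing them towards a fixed final number makes it easy to report on finishers alone. An analysis plan cannot repair this later, because it cannot analyse events that no visit asked about. Meanwhile the protocol's own account of the expected risk is inconsistent, so the reader cannot tell what the sponsor expected to see.

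**Working it through.** **1. Contacts.** Table 1 numbers visits 1–9 in the first period and 10–17 in the second: 9 + 8 = 17, which reproduces the stated 17. Visits 3 and 11 are phone calls, leaving 15 clinic visits. Without Screening, which precedes any exposure, 16 contacts remain.

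**2. Adverse-event items.** Table 1 has 18 procedure rows, and none records adverse events or device incidents. The count is 0 of 17 contacts, or 0 of 16 from Baseline onward. Neither the outcomes section nor the Data sets section adds one.

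**3. What could show harm indirectly** (counts from Table 1 and the Methodology text):

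| Source | Contacts | Limit |
|---|---|---|
| Symptom scale | 4 + 4 = 8 | Ten symptoms linked to limb swelling; Baseline, Week 3 and two follow-ups only |
| Diary review | 5 + 5 = 10 | Content not described; not among the listed data sets |
| Vital signs | 8 + 7 = 15 | Recorded at visits, but not among the listed data sets |
| Concomitant medications | 8 + 7 = 15 | Not among the listed data sets |
| Feedback call | 1 + 1 = 2 | Unstructured; Day 1 or 2 only |
| Comments on the pad | After 3 weeks of use | Come from those who reach that point |
| Physical exam | 2 + 1 = 3 | Visits 1, 2 and 10; none during the three weeks of use |

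None of these defines an event, asks about it in the same way in both conditions, or yields a rate.

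**4. The early leaver.** Four contacts lie between Baseline and Week 3 (visits 3–6, or 11–14). Someone who stops in that window has no on-treatment symptom score and is not reached by the end-of-use comments. What remains is one call, up to four diary reviews, and vital signs and medications at up to three visits.

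**5. The denominator.** Suppose k people leave for discomfort and each is replaced completely, so that 30 finish. The rate among starters is k/(30 + k). Among final participants only, it is 0/30. The protocol gives no expected number of withdrawals, so k is assumed:

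| k | Among starters | Among final 30 |
|---|---|---|
| 1 | 1/31 = 3.2% | 0% |
| 2 | 2/32 = 6.3% | 0% |
| 3 | 3/33 = 9.1% (exact 95% CI 1.9% to 24.3%) | 0% |
| 5 | 5/35 = 14.3% | 0% |

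The protocol does not say which column would be reported.

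**6. Risk statements side by side.** Ethical considerations denies any risk of discomfort, then makes discomfort the foreseeable risk and adds possible distress. The risk-management answer provides for people who find the treatment uncomfortable. The Consent section says low risk, not none. The denial cannot stand with the other statements.

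**The case against.** The strongest reply is that the plan does not ignore harm. Finishers rate ten symptoms, including cramps and burning, at eight contacts. Vital signs and medications are taken at 15, the diary is reviewed at 10, and feedback is stored and summarised by theme. Withdrawal is not the only safeguard either: counselling is offered, a Day 1 or 2 call checks pad placement, the exclusion criteria cover pacemakers, large metal implants, wounds and recent cellulitis, and limb conditions can be observed. The aims contain no safety objective. How leavers are counted is commonly left to a statistical analysis plan, which is not shown.

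Most of this stands, and it rules out several stronger readings that a reader might infer:

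- *The no-risk statement can never be tested, or finishers look problem-free by construction.* Not supported, because the sources above can reveal problems.
- *Leavers give no reason and vanish from the results.* Not supported. The withdrawal is documented, a reason may be given, and replacement may apply to one arm only. No passage excludes leavers from reporting; the protocol leaves it open.
- *Replacement targets those who leave for discomfort.* It applies to every withdrawal.
- *The upper limit after zero events in 30 measures the defect.* That one-sided 95% limit is 1 − 0.05^(1/30) = 9.5%. It would be the same with perfect recording, so it shows what 30 people can tell us about risk, not what the missing row costs.

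The reply does not supply a defined, routinely asked event item in both conditions. Collection is fixed by the visit schedule, not by the analysis plan.

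**Conclusion.** The point holds in a limited form. Adverse-event or device-incident items are scheduled at 0 of 17 contacts. Harms would be captured unsystematically, without a rate by condition, and least well for people who stop before Week 3. Because leavers are replaced and the reason is optional, a tolerability figure could differ between starters and final participants. With one to five such leavers (assumed), the rate among starters would be 3.2% to 14.3%, against 0% among the final 30. That gap arises only if leavers are left out of the denominator, which the protocol neither states nor prevents. The risk statements contradict each other and must be reconciled.

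This rests on Table 1 and the Data sets section being the full account of what is collected. It concerns safety information and does not by itself affect the efficacy comparison. It should be corrected prospectively, since events that were not asked about cannot be reliably recovered afterwards.

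**What to change.** 1. Add an adverse-event and device-incident row to Table 1 at every contact from Baseline onward, in both conditions, using the visits, calls and diary reviews already scheduled. Add the item to the Data sets section.
2. State that events and withdrawals, with any reason volunteered, will be reported by condition for everyone who started that condition, including those later replaced. Giving a reason stays voluntary.
3. Reconcile the risk statements in the Consent section, the Ethical considerations section and the risk-management answer so that they agree.

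The cost is one extra question per contact (16 per participant from Baseline onward) and one extra results table. No extra visit is needed.
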